5.0 METHODOLOGY

5.1 Entry Criteria

5.1.1 Diagnosis/Condition for Entry into the Trial

Eligible patients must:

- Have a histologically confirmed diagnosis of follicular lymphoma, diffuse large B-cell lymphoma, or classical Hodgkin lymphoma according to the WHO classification, with hematopathology review at the participating institution.
 - FL: grade 1, 2, 3A, or 3B are eligible.
 - DLBCL: transformed indolent lymphomas (TIL), primary mediastinal large B-cell lymphoma (PMBCL), and aggressive B-cell lymphoma unclassified (BCL-U) are eligible.
 - HL: all classical HL subtypes are eligible except for nodular lymphocyte predominant Hodgkin lymphoma, which is excluded.

NOTE: Per Amendment (Protocol V9 dated 06-04-20), this study will only enroll HL patients who have had prior exposure to PD-1/PD-L1 immunotherapy. FL, DLBCL, and HL patients without prior exposure to PD-1/PD-L1 immunotherapy are no longer eligible.

- Patients with HL or DLBCL must refuse or not be candidates for curative autologous stem cell transplantation.
- Have relapsed or refractory disease after at least 1 prior regimen, including:
 - Recurrence of disease after a documented complete response (CR)
 - Progression of disease after a partial response (PR) to the prior regimen
 - Partial response (PR), stable disease (SD) or progressive disease (PD) at the completion of the prior treatment regimen. If a patient has PR to prior regimen without PD, there must be biopsy-proven residual disease that is measurable.

NOTE: Per Amendment (Protocol V10 dated 10-16-20), this study will only enroll HL patients who are refractory to PD-1/PD-L1 immunotherapy.

Refractory to PD-1/PD-L1 immunotherapy is defined as patients who had prior exposure to PD-1/PD-L1 immunotherapy and either - achieved a best response of SD or PD or - achieved a best response of CR/PR but developed PD while on active PD-1/PD-L1 treatment.

5.1.2 Subject Inclusion Criteria

In order to be eligible for participation in this trial, the subject must:

1. Documented informed consent of the participant or legally authorized representative.
2. Be ≥ 18 years of age on day of signing informed consent.
3. Have measurable disease by CT or PET scan, with one or more sites of disease ≥ 1.5 cm in longest dimension.
4. Be willing to provide tissue from a fresh core or excisional biopsy of a tumor lesion prior to starting study therapy or from archival tissue of a biopsy that was performed after the most recent systemic therapy.
5. Have a performance status of 0 or 1 on the ECOG Performance Scale.
6. Demonstrate adequate organ function as defined in Table 1, all screening labs should be performed within 14 days of treatment initiation.

Table 1. Adequate Organ Function Laboratory Values

System	Laboratory Value
Hematological	
Absolute neutrophil count (ANC)	$\geq 1,000 / \text{mcL}$ Exception: Unless documented bone marrow involvement by lymphoma.
Platelets	$\geq 75,000 / \text{mcL}$ Exception: Unless documented bone marrow involvement by lymphoma.
Hemoglobin	$\geq 8 \text{ g/dL}$ without transfusion or EPO dependency (within 7 days of assessment) Exception: Unless documented bone marrow involvement by lymphoma.
Renal	
Serum creatinine OR Measured or calculated ^a creatinine clearance (GFR can also be used in place of creatinine or CrCl)	$\leq 1.5 \times$ upper limit of normal (ULN) OR $\geq 60 \text{ mL/min}$ for subject with creatinine levels $> 1.5 \times$ institutional ULN
Hepatic	
Serum total bilirubin	$\leq 1.5 \times$ ULN or $\leq 3 \times$ ULN if patient has Gilbert's disease OR Direct bilirubin \leq ULN for subjects with total bilirubin levels > 1.5 ULN
AST (SGOT) and ALT (SGPT)	$\leq 2.5 \times$ ULN OR $\leq 5 \times$ ULN for subjects with liver involvement by lymphoma as the etiology of transaminase elevation
Albumin	$\geq 2.5 \text{ mg/dL}$
Coagulation	

International Normalized Ratio (INR) or Prothrombin Time (PT)	$\leq 1.5 \times \text{ULN}$ unless subject is receiving anticoagulant therapy as long as PT or PTT is within therapeutic range of intended use of anticoagulants
Activated Partial Thromboplastin Time (aPTT)	$\leq 1.5 \times \text{ULN}$ unless subject is receiving anticoagulant therapy as long as PT or PTT is within therapeutic range of intended use of anticoagulants

^aCreatinine clearance should be calculated by the Cockcroft-Gault equation

7. Female subject of childbearing potential should have a negative urine or serum pregnancy within 72 hours prior to receiving the first dose of study medication. If the urine test is positive or cannot be confirmed as negative, a serum pregnancy test will be required.
8. Female subjects of childbearing potential (Section 7.11.2) must be willing to use an adequate method of contraception as outlined in Section 7.11.2 – Contraception, for the course of the study through 120 days after the last dose of study medication.

Note: Abstinence is acceptable if this is the usual lifestyle and preferred contraception for the subject.

9. Male subjects of childbearing potential (Section 7.11.2) must agree to use an adequate method of contraception as outlined in Section 7.11.2- Contraception, starting with the first dose of study therapy through 120 days after the last dose of study therapy.

Note: Abstinence is acceptable if this is the usual lifestyle and preferred contraception for the subject.

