7.2 Definition of Dose-Limiting Toxicity

The dose-limiting toxicity (DLT) observation period will be 42 days (2 cycles). DLT assessment will occur on cycle 3, day 1 prior to receipt of cycle 3, day 1 of study therapy. Toxicities will be graded according to the National Cancer Institute Common Terminology Criteria for Adverse Events (CTCAE, Version 4.03) accessible at:

http://evs.nci.nih.gov/ftp1/CTCAE/CTCAE_4.03_2010-06-14_QuickReference_5x7.pdf

DLT will be defined as one of the following AEs that is at least possibly related to study treatment.

Hematologic

- Grade 4 neutropenia lasting > 7 days (despite the use of growth factor support).
- Grade 4 thrombocytopenia lasting > 7 days or requiring platelet transfusion.
- Grade 3 or 4 thrombocytopenia associated with grade 2 or higher bleeding.
- Grade 4 anemia not associated with lymphoma.

- Any Grade 5 AE.

Non-hematologic

- Grade ≥ 3 pneumonitis that does not resolve to grade ≤ 1 within 3 days after initiation of supportive care measures.
- Any clinically relevant grade 3 or grade 4 AE with the exception of:
 - Grade 3 asymptomatic laboratory abnormalities, including lipase or amylase, that are not clinically relevant, not requiring hospitalization or delay of treatment.
 - Grade 4 laboratory abnormalities including, but not limited to, hypo- or hyperglycemia, hypo- or hypernatremia, hypo- or hyperkalemia, hypo- or hypermagnesemia, hypo- or hyperphosphatemia, or hyperuricemia that resolve within 48 hours to Grade ≤ 2 with supportive measures.
 - Grade 3 nausea, or fatigue controlled with supportive measures.
 - Grade 3 vomiting if the subject does not require total parenteral nutrition (TPN), tube feeding, or hospitalization, and the toxicity improves to $<$ grade 3 within 72 hours.
 - Grade 3 asymptomatic endocrinopathy.
 - Grade 3 fatigue related to endocrinopathy that resolves within 7 days of hormone-replacement or corticosteroid therapy.
 - Grade 3 local inflammatory response attributed to local antitumor response.
 - Vitiligo or alopecia of any grade.
- Any Grade 5 AE.

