7.9.1 Acceptable Concomitant Medications

All treatments that the investigator considers necessary for a subject's welfare may be administered at the discretion of the investigator in keeping with the community standards of medical care. All concomitant medication will be recorded on the case report form (CRF) including all prescription, over-the-counter (OTC), herbal supplements, and IV medications and fluids. If changes occur during the trial period, documentation of drug dosage, frequency, route, and date may also be included on the CRF.

All concomitant medications received within 28 days before the first dose of trial treatment and 30 days after the last dose of trial treatment should be recorded. Concomitant medications administered after 30 days after the last dose of trial treatment should be recorded for SAEs and ECIs.

Use of growth factors, including filgrastim or pegfilgrastim and erythropoietin, is permitted per institutional policy and in accordance with American Society of Clinical Oncology (ASCO) guidelines.¹³⁸ Red blood cell transfusions are permitted per institutional guidelines. Platelet transfusions are permitted, but will be considered a DLT if required during the DLT period.

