- **Expected Adverse Event** - An adverse event is expected if it does not meet the criteria for an unexpected event, OR is an expected natural progression of any underlying disease, disorder, condition, or predisposed risk factor of the research participant experiencing the adverse event.
- **Adverse Event Attribution**

The following definitions will be used to determine the causality (attribution) of the event to the study agent or study procedure.

 - **Unrelated** – The event is clearly related to other factors such as the participant's clinical state, other therapeutic interventions, or concomitant medications administered to the participant.
 - **Unlikely** – The event is doubtfully related to the investigational agent(s). The event was most likely related to other factors such as the participant's clinical state, other therapeutic interventions, or concomitant drugs.
 - **Possible** – The event follows a reasonable temporal sequence from the time of drug administration, but could have been produced by other factors such as the participant's clinical state, other therapeutic interventions, or concomitant drugs.
 - **Probable** – The event follows a reasonable temporal sequence from the time of drug administration, and follows a known response pattern to the study drug.

The event cannot be reasonably explained by other factors such as the participant's clinical state, therapeutic interventions, or concomitant drugs.

- **Definite** – The event follows a reasonable temporal sequence from the time of drug administration, follows a known response pattern to the study drug, cannot be reasonably explained by other factors such as the participant's condition, therapeutic interventions, or concomitant drugs, AND occurs immediately following study drug administration, improves upon stopping the drug, or reappears on re-exposure.
- **Unanticipated Problem (UP)** – Any incident, experience, or outcome that meets all three of the following criteria:
 - Unexpected (in terms of nature, severity, or frequency) given the following: a) the research procedures described in the protocol-related documents such as the IRB approved research protocol, informed consent document or Investigator Brochure (IB); and b) the characteristics of the subject population being studied; AND

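### Table 1 waives three blood-count limits for marrow involvement, but only the anaemia DLT sets lymphoma-related events aside, and the platelet-transfusion sentence has no attribution condition

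*Combined protocol and SAP*

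**What the plan says.** **Entry.** Table 1 in section 5.1.2 sets minimums for ANC (1,000/mcL), platelets (75,000/mcL) and haemoglobin (8 g/dL). Each carries the same waiver: "Exception: Unless documented bone marrow involvement by lymphoma". No lower value replaces the waived one.

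**DLT definition.** Section 7.2 opens with a general condition: "DLT will be defined as one of the following AEs that is at least possibly related to study treatment". Its haematologic lines include "Grade 4 neutropenia lasting > 7 days (despite the use of growth factor support)" and "Grade 4 thrombocytopenia lasting > 7 days or requiring platelet transfusion", plus Grade 3 or 4 thrombocytopenia with bleeding of Grade 2 or more. None of these refers to baseline or to marrow disease. The anaemia line does: "Grade 4 anemia not associated with lymphoma".

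**Transfusion.** Section 7.9.1, repeated in 7.10.1, says: "Platelet transfusions are permitted, but will be considered a DLT if required during the DLT period". It states no grade, attribution or baseline condition.

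**Attribution.** Section 14.1 defines *Possible* as: "The event follows a reasonable temporal sequence from the time of drug administration, but could have been produced by other factors". The participant's clinical state is among the other factors it lists.

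**Decision rule.** Under section 7.1.2, two patients with a DLT end escalation at a level, and the MTD allows at most 1 in 6. Section 7.3 states the limit as below 33% with at least six treated.

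**The concern.** Three lineages are waived at entry, but the DLT list handles the resulting confounding for only one of them. A patient admitted with low neutrophils or platelets from marrow disease could then be counted as a DLT by two routes:

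- **Through 7.2.** A cytopenia of unclear cause can be graded *Possible*, and that satisfies the attribution condition. Section 4.5.6 lists neutropenia and thrombocytopenia as effects of vorinostat, so a grade of *Unlikely* may be hard to defend.
- **Through 7.9.1 and 7.10.1.** Read literally, a transfusion needed because of marrow disease is a DLT whatever its cause.

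The rule tolerates one DLT in six. One disease-related event uses up that tolerance and pushes the MTD and RP2D downward. Determining both is a primary objective.

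**Working it through.** **The plan's own threshold.** 1/6 = 16.7%, which is below 33% and passes. 2/6 = 33.3%, which is not below 33% and fails. Sections 7.1.2 and 7.3 therefore agree that a second DLT closes a level of six.

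**The texts applied to two cases, each a patient admitted under the platelet waiver.**

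| Case | Under 7.2 | Under 7.9.1 and 7.10.1 |
|---|---|---|
| Transfused in the DLT period; event judged *Unrelated* (marrow disease) | Not a DLT: fails the attribution condition | DLT |
| Grade 4 platelets for more than 7 days, worsening on treatment, cause unclear, graded *Possible*; no transfusion | DLT | Not addressed |

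The first case is a direct conflict. The second shows the asymmetry: for Grade 4 anaemia the same doubt could be settled by the lymphoma qualifier, but for platelets or neutrophils there is no such qualifier.

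**Effect on closing a level.** Inputs: six evaluable patients and closure at two DLTs (section 7.1.2). Two further inputs are assumptions, because the documents give neither:

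- p, the true DLT risk per patient;
- q, the chance that one marrow-involved patient has a disease cytopenia counted as a DLT.

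That patient's DLT probability is 1 − (1 − p)(1 − q), and the other five have p. The chance of two or more DLTs reduces to

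P(close) = 1 − (1 − p)^5 − (1 − q) × 5p(1 − p)^5.

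At p = 0.15, (0.85)^5 = 0.4437, so P(close) = 0.5563 − (1 − q) × 0.3328. At p = 0.10, (0.90)^5 = 0.5905, so P(close) = 0.4095 − (1 − q) × 0.2952.

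| p | q = 0 | q = 0.25 | q = 0.5 | q = 1 (ceiling) |
|---|---|---|---|---|
| 0.10 | 11.4% | 18.8% | 26.2% | 41.0% |
| 0.15 | 22.4% | 30.7% | 39.0% | 55.6% |

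The q = 0 column is the ordinary binomial chance of two or more in six. Section 7.1.2 also permits escalation after three patients without a DLT. If that option is always taken, the q = 0 figures fall to 9.4% and 18.6%. Six patients is the relevant case for declaring an MTD.

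**The case against.** The plan has real safeguards, and most of the case against stands.

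- **Attribution.** Under 14.1, events graded *Unrelated* or *Unlikely* fail the condition in 7.2, and 7.1.2 again speaks of DLTs attributable to treatment. Even *Possible* requires a reasonable time relation to dosing. An adverse event must also be an untoward experience or a change in an existing condition, so a stable low baseline count arguably does not qualify. A reader might infer that 7.2 turns disease cytopenia into a DLT automatically; the text does not support that.
- **Entry discretion.** Exclusion 17 in section 5.1.3 lets the treating investigator exclude a laboratory abnormality that could confound results. It gives no numeric floor, but entry is not unconditional.
- **Caution.** Counting an on-treatment fall of unclear cause can be defended as conservative, because vorinostat itself lowers platelets.
- **Timing.** Section 4.6.4 reports 42 patients enrolled, while escalation allows at most 4 levels × 6 = 24 evaluable patients and expects 12 (section 11.3). Escalation appears finished. Remaining accrual is Hodgkin lymphoma, for which no screening marrow biopsy is required (section 8.1, footnote j).

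These points narrow the concern but do not remove it. *Possible* still admits disease as the alternative cause, and the transfusion sentence bypasses attribution. The definition in 7.2 also remains in use, because sections 7.1.1 and 7.12 refer to it for ending treatment.

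**Conclusion.** The point holds as an inconsistency of text. Three entry limits are waived, one lineage is protected in the DLT list, and the transfusion sentence in 7.9.1 and 7.10.1 contradicts the attribution condition in 7.2. Followed as written, the plan can count disease cytopenia as a DLT.

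With one affected patient in six and p = 15%, the chance of closing the level rises from 22% to 31% (q = 0.25) or 39% (q = 0.5). At p = 10% it rises from 11% to 19% or 26%. The values 56% and 41% are ceilings that assume the spurious DLT is certain, and should not be read as the expected effect. All these figures rest on assumed p and q.

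A reader might also infer that the MTD or RP2D actually reached is too low. The documents do not support that: they report neither the DLTs observed nor how many escalation patients used the waiver. The direction of any bias from a spurious DLT is downward, but whether it occurred is unknown.

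**What to change.** 1. Reconcile 5.1.2, 7.2, 7.9.1 and 7.10.1. The neutropenia, thrombocytopenia and platelet-transfusion criteria should carry the same lymphoma qualifier as the anaemia line, and the transfusion sentence should be subject to the attribution condition of 7.2. This concerns only what is counted as a DLT; no count threshold or transfusion practice is proposed.
2. Check the line in section 10.2 covering other adverse events of Grade 4 or above. It requires at least a possible relation to treatment but has no lymphoma or baseline qualifier, and it feeds the accrual halt in 11.2 (more than 3 events in the first 12 patients, or a rate of 33% or more later).
3. Since escalation appears complete, report baseline counts and waiver status for each haematologic DLT that informed the MTD or RP2D.

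A separate category of patients evaluable only for non-haematologic DLT should not be added: Table 4 works from a single evaluable count and section 7.4 has no such class.

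**Cost.** Wording changes and a short listing. The main downside is that a real vorinostat cytopenia in a marrow-involved patient could be put down to disease, which would bias the MTD upward. The basis for each such attribution should therefore be recorded.

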5.1.3 Subject Exclusion Criteria

The subject must be excluded from participating in the trial if the subject:

1. Is currently participating and receiving study therapy or has participated in a study of an investigational agent and received study therapy or used an investigational device within 3 weeks of the first dose of treatment.
2. Has a diagnosis of immunodeficiency or is receiving systemic steroid therapy or any other form of immunosuppressive therapy within 7 days prior to the first dose of trial treatment.
3. Has received a prior allogeneic hematopoietic stem cell transplant within the past 5 years, requires immunosuppression, or has evidence of active graft-versus-host-disease.
4. Has received prior autologous hematopoietic stem cell transplant within the last 60 days.

5. Has a known history of active TB (Bacillus Tuberculosis)
6. Severe hypersensitivity to pembrolizumab or any of its excipients.
7. Has had a prior anti-cancer monoclonal antibody (mAb) within 3 weeks prior to study Day 1 or who has not recovered (i.e., \leq Grade 1 or at baseline) from adverse events due to agents administered more than 3 weeks earlier. If a patient has progressive or stable disease to prior regimen, rituximab is allowed up to 2 weeks prior to the initiation of study therapy.
8. Has had prior chemotherapy, targeted small molecule therapy, or radiation therapy within 2 weeks prior to study Day 1 or who has not recovered (i.e., \leq Grade 1 or at baseline) from adverse events due to a previously administered agent.
 - Note: Subjects with \leq Grade 2 neuropathy are an exception to this criterion and may qualify for the study.
 - Note: If subject received major surgery, they must have recovered adequately from the toxicity and/or complications from the intervention prior to starting therapy.
9. Has taken valproic acid, or another histone deacetylase inhibitor, within 2 weeks prior to study Day 1.
10. Has a known additional malignancy that is progressing or requires active treatment. Exceptions include basal cell carcinoma of the skin or squamous cell carcinoma of the skin that has undergone potentially curative therapy or in situ cervical cancer.
11. Has known active central nervous system (CNS) involvement by lymphoma, including leptomeningeal involvement. Subjects with prior CNS involvement by lymphoma must have remission of the CNS component of the lymphoma. These subjects must have a baseline MRI during screening without evidence of new or enlarging brain lesions and must not have any new or progressive neurologic symptoms.
12. Has active autoimmune disease that has required systemic treatment in the past 2 years (i.e. with use of disease modifying agents, corticosteroids or immunosuppressive drugs). Replacement therapy (eg., thyroxine, insulin, or physiologic corticosteroid replacement therapy for adrenal or pituitary insufficiency, etc.) is not considered a form of systemic treatment. A history of hemolytic anemia associated with the lymphoma does not exclude a patient from the study.
13. Has a history of (non-infectious) pneumonitis that required steroids or current pneumonitis
14. Has an active infection requiring systemic therapy.

15. Has a QT interval corrected for heart rate (QTc) > 470 ms using the Fridericia formula. If the screening electrocardiogram (ECG) has a QTc > 470ms, the mean QTc of 3 ECGs can be utilized, but must be < 470 ms.
16. Is unable to swallow capsules, has a partial or small bowel obstruction, or has a gastrointestinal condition resulting in a malabsorptive syndrome (e.g. small bowel resection with malabsorption).
17. Has a history or current evidence of any condition, therapy, or laboratory abnormality that might confound the results of the trial, interfere with the subject's participation for the full duration of the trial, or is not in the best interest of the subject to participate, in the opinion of the treating investigator.
18. Has known psychiatric or substance abuse disorders that would interfere with cooperation with the requirements of the trial.
19. Is pregnant or breastfeeding, or expecting to conceive or father children within the projected duration of the trial, starting with the pre-screening or screening visit through 120 days after the last dose of trial treatment.
20. Has a known history of Human Immunodeficiency Virus (HIV) (HIV 1/2 antibodies).
21. Has known active Hepatitis B (e.g., HBsAg reactive) or Hepatitis C (e.g., HCV RNA [qualitative] is detected).
22. Has received a live vaccine within 30 days of planned start of study therapy.

Note: Seasonal influenza vaccines for injection are generally inactivated flu vaccines and are allowed; however intranasal influenza vaccines (e.g., Flu-Mist®) are live attenuated vaccines, and are not allowed.

